13.4 Tertiary Efficacy Endpoints

The following additional patient-reported outcomes (PROs) will be used to assess HRQoL during the study:

- Change from baseline in other domain scores of HAEMO-QoL-A (Worry, Emotional impact, Treatment concern) at Week 104 of the study post-BMN 270 infusion
- Change from baseline in the EQ-5D-5L score at Week 104 of the study post-BMN 270 infusion
- Change from baseline in the Haemophilia Activities List (HAL) score at Week 104 of the study post-BMN 270 infusion
- Change from baseline in the Work Productivity and Activity Impairment plus Classroom Impairment Questions: Hemophilia Specific (WPAI+CIQ:HS) score at Week 104 of the study post-BMN 270 infusion
- Change from baseline in Patient Reported Outcomes, Burdens, and Experiences (PROBE) score at Week 104 of the study post-BMN 270 infusion

The PROs will be assessed at baseline, Week 4, Week 12, Week 26, Week 52 and every 6 months starting with Week 76 per protocol-scheduled assessments.

The tertiary endpoints (except for PROBE) will be summarized descriptively by visit up to the data cut-off. The p-value and 95% CI for the change from baseline based on two-sided t-test will be provided. The p-value is considered descriptive. PROBE will be analyzed externally through a separate statistical analysis plan.

13.4.1 Analysis Methods for Other Domain Scores of Haemo-QoL-A

The primary analyses of other Haemo-QoL-A domain scores (Worry, Emotional impact, Treatment concern) will be based on the mITT population using observed cases.

**Study 270-301 Statistical Analysis Plan**

Each of the Haemo-QoL-A domain score will be analyzed using an MMRM approach. The model will include visit (baseline, Week 4, Week 12, Week 26, Week 52, Week 76, Week 104) as the only factor and will use an unstructured covariance matrix. The LS mean change from baseline to Week 104 will be reported. The domain scores will also be summarized descriptively by visits. A graphical summary of mean change over time will be provided.

13.4.2 Analysis Methods for EQ-5D-5L

The EQ-5D-5L index score (using appropriate country-based Crosswalk value sets, version 24OCT2019, referring Van Hout et al. 2012) and visual analog scale (VAS) will be analyzed for the mITT population with observed cases using the same analysis methods as Haemo-QoL-A. The number and percentage of subjects reporting each level of problem on each dimension of the EQ-5D-5L will be provided over time.

13.4.3 Analysis Methods for HAL

The HAL summary scores (upper extremity activities, basic lower extremity activities, complex lower extremity activities, overall) will be analyzed for the mITT population with observed cases using the same analysis methods as the Haemo-QoL-A total score.

The HAL domain scores (lying/sitting/kneeling/standing, functions of the legs, functions of the arms, use of transportation, self-care, household tasks, leisure activities and sports) will be summarized descriptively for the mITT population using observed cases.

13.4.4 Analysis Methods for WPAI+CIQ: HS

The following variables will be summarized descriptively over time for the mITT population using observed cases:

- Percent work time missed due to problems associated with hemophilia
- Percent impairment while working due to problems associated with hemophilia
- Percent overall work impairment due to problems associated with hemophilia
- Percent class time missed due to problems associated with hemophilia
- Percent impairment in the classroom due to problems associated with hemophilia
- Percent overall classroom impairment due to problems associated with hemophilia
- Percent activity impairment due to problems associated with hemophilia

13.4.5 Analysis Methods for PROBE

PROBE will be analyzed externally through a separate statistical analysis plan.

13.5 Other Efficacy Endpoints

13.5.1 FVIII infusions

Total and annualized number of FVIII infusions will be listed by subject and by periods (pre--BMN 270 infusion [baseline period], Weeks 1-4, Week 1 to end of FVIII prophylaxis, Post FVIII Prophylaxis-52, Weeks 53-104, and the efficacy evaluation periods as defined in [Table 13.1.1](#)), and the annualized rates will be summarized descriptively by periods.

The same analysis of FVIII utilization (IU/kg) and number of FVIII infusions will be performed for the following types of FVIII infusion in the primary efficacy evaluation period:

- Treatment for bleed
- Surgery/procedure
- Usual prophylaxis (routine)
- One-time prophylaxis

Analysis based on the type of FVIII product used will be performed if applicable.

13.5.2 Bleeds

The following types of bleeds will be analyzed:

- All bleeds, including both treated and non-treated
- Treated joint bleeding episodes
- Treated target joint bleeding episodes (bleeding episodes that occur at joints which are listed as target joints at study entry)
- Treated spontaneous bleeding episodes
- Treated traumatic bleeding episodes

The analyses include tabulation of total and annualized counts by subject and by periods (pre--BMN 270 infusion, Weeks 1-end of FVIII Prophylaxis, Post FVIII Prophylaxis-52, Weeks 53-104, and the efficacy evaluation periods as defined in [Table 13.1.1](#)), and descriptive summary of the corresponding annualized rates. Target joint resolution with the incidence and percentage of the resolved target joints post BMN-270 treatment will be assessed.

13.6 Examination of Efficacy by Subgroups

The following subgroup analyses may be examined for the primary and secondary efficacy endpoints:

- Age at enrollment: ≥ 18 - < 30 years vs. ≥ 30 - < 50 years vs. ≥ 50 years old
- Race: Asian, Black or African American, White, Other
- Target joints at baseline: Yes vs No
- Region: Europe/Middle East, North America, South America, Africa, Australia, East Asia

Subgroup analyses based on other baseline characteristics may also be performed.

13.7 Interim Analysis and Multiplicity Adjustment

Prior to this 2-year analysis, two protocol-specified interim analyses and a 1-year analysis were planned, of which one interim analysis and the 1-year analysis were performed.

Two interim analyses were planned after approximately 16 and 20 treated HIV-negative subjects have completed the Week 26 visit (or have discontinued study prior to Week 26), respectively. The concept of the interim analyses was to facilitate initiation of regulatory review of the ongoing study in the event that robust improvements (essentially normalization) in Factor VIII activity in a sufficient proportion of the subjects are observed.

Study 270-301 Statistical Analysis Plan

The primary efficacy endpoint was subject's FVIII response status, where a subject was considered as a responder if the median FVIII activity per chromogenic assay during Weeks 23-26 post-BMN 270 infusion is ≥ 40 IU/dL. The alpha levels of 0.0002 and 0.001 were allocated to the first and second interim analysis, respectively. The second interim analysis would only occur if the result from the first interim analysis was not positive (i.e., if the pre-specified statistical significance was not achieved). A 1-year analysis was planned after all subjects have been followed for 52 weeks post-BMN 270 infusion (or have discontinued study prior to Week 52). The efficacy endpoints included change from baseline (prior to BMN 270 infusion while receiving FVIII prophylaxis) in ABR for treated bleeds, change from baseline (assuming no treatment for severe hemophilia A) in FVIII activity per chromogenic assay at Weeks 49-52, and change from baseline (prior to BMN 270 infusion while receiving FVIII prophylaxis) in annualized FVIII utilization. These endpoints were tested sequentially using a hierarchical testing procedure at the alpha level determined by the fallback procedure (Wiens, 2005) to control the family-wise type I error rate at 0.05. Results from this analysis were intended to support regulatory submissions to EMA and other health authorities outside of FDA.

The first interim analysis was performed in May 2019 (data cut-off date: 30 April 2019) after 16 directly enrolled, HIV-negative subjects have completed the Week 26 visit. Based on the analysis results ($p=0.001$) and the totality of the data, the secondary interim analysis was deemed unnecessary (the test would be statistically significant at the pre-specified significance level of 0.001) and therefore never implemented. The 1-year analysis was performed in January 2021 (data cut-off date: 16 November 2020) after all subjects had been followed for 52 weeks post-BMN 270 infusion. Results from all pre-specified tests were statistically significant ($p < 0.0001$) at the alpha level of 0.0498 that was determined by the fallback procedure (SAP version 3.0, dated 17 December 2020).

- If the first interim p-value ≤ 0.0002 , the first interim result is declared significant and the 1-year analysis is carried out at the 0.05 level.
- If the first interim p-value > 0.0002 , the first interim result is not declared significant and the second interim analysis is carried out at 0.001 level. If the second interim p-value ≤ 0.001 , the second interim result is declared significant and the 1-year analysis is carried out at the 0.0498 level.
- If the second interim p-value > 0.001 , the interim results are not declared significant and the 1-year analysis is carried out at the 0.0488 level.

As specified in the 1-year analysis SAP (version 3.0, dated 17 December 2020), in the event that a 2-year final analysis is necessary, the testing procedure used in the 1-year analysis will be extended to the 2-year final analysis. That is, when all pre-specified tests (ie.

Study 270-301 Statistical Analysis Plan

Non-inferiority test of BMN 270 vs. FVIII prophylaxis in ABR with a NI margin of 3.5, superiority test of BMN 270 vs. no treatment for severe hemophilia A in FVIII activity, superiority test of BMN 270 versus FVIII prophylaxis in FVIII utilization, superiority test of BMN 270 vs. FVIII prophylaxis in ABR) are statistically significant at the 1-year analysis, the corresponding efficacy endpoints at 2 years will be tested in the same sequence Per FDA's recommendation, the 2-year final analysis will be performed at the significance level of 0.05. The efficacy endpoints will be tested in the following hierarchical testing sequence:

1. For non-inferiority of BMN 270 versus FVIII prophylaxis in ABR (treated bleeds) with a NI margin of 3.5
Null hypothesis: post-baseline ABR – baseline ABR ≥ 3.5
2. For superiority of BMN 270 versus no treatment for severe hemophilia A in FVIII activity
Null hypothesis: FVIII activity at Week 104 – baseline FVIII activity ≤ 0
3. For superiority of BMN 270 versus FVIII prophylaxis in FVIII utilization
Null hypothesis: post-baseline FVIII utilization – baseline FVIII utilization ≥ 0
4. For superiority of BMN 270 versus FVIII prophylaxis in ABR (treated bleeds)
Null hypothesis: post-baseline ABR – baseline ABR ≥ 0
5. For superiority of BMN 270 versus FVIII prophylaxis in ABR (all bleeds)
Null hypothesis: post-baseline ABR – baseline ABR ≥ 0
6. For superiority of BMN 270 versus FVIII prophylaxis in Haemo-QoL-A Total score
Null hypothesis: post-baseline total score at Week 104 – baseline total score ≥ 0
7. For superiority of BMN 270 versus FVIII prophylaxis in Haemo-QoL-A Physical functioning domain score
Null hypothesis: post-baseline physical functioning score at Week 104 – baseline physical functioning score ≥ 0
8. For superiority of BMN 270 versus FVIII prophylaxis in Haemo-QoL-A Consequences of bleeding domain score
Null hypothesis: post-baseline Consequences of bleeding score at Week 104 – baseline Consequences of bleeding score ≥ 0
9. For superiority of BMN 270 versus FVIII prophylaxis in Haemo-QoL-A Role functioning domain score

Study 270-301 Statistical Analysis Plan

Null hypothesis: post-baseline Role functioning score at Week 104 – baseline Role functioning score ≥ 0

After the 2-year final analysis, safety and efficacy will then continue to be assessed long-term in all subjects for a total of approximately 5 years.

14 SAFETY EVALUATIONS

Safety will be assessed by adverse event reporting; clinical laboratory assessments, with particular attention to the liver tests; vital signs assessments; physical examinations; and immunogenicity. Safety analyses will be carried out for the ITT analysis population. No formal statistical testing will be performed; only summary statistics will be provided.

14.1 Adverse Events

Only treatment-emergent adverse events (TEAEs) occurring and reported during the study period will be included in the adverse event summaries. A TEAE is defined as any AE that newly appeared or worsened in severity following initiation of study drug administration. Adverse events will be coded in accordance with Medical Dictionary for Regulatory Activities (MedDRA).

An adverse drug reaction (ADR) is any AE for which there is a reasonable possibility that the study drug caused the AE. The investigator will assess the causality for individual AEs, applying the guidance specified in protocol, and those assessed as investigational-product-related will be considered ADRs.

A serious adverse event (SAE) is any untoward medical occurrence that at any dose meets one or more of the seriousness criteria enumerated in the protocol. AE severity, not equivalent to seriousness, will be assessed using the protocol defined categories using the NCI CTCAE v4.03.

All bleeding events and suspected bleeding events, regardless of the need for exogenous FVIII therapy as treatment, should be captured in subject diaries and recorded on the designated bleeding eCRF. Bleeding events and suspected bleeding events should not be reported as adverse events, with the following exception:

- All bleeding events and suspected bleeding events which meet one or more of the criteria for being serious (refer to the protocol Section 10.2) should be reported as serious adverse events (whether or not they are bleeding events that are normal sequelae of hemophilia, and whether or not they require exogenous FVIII as treatment).

The study AE reporting period is as follows: After informed consent but prior to initiation of study treatment, only SAEs associated with any protocol-imposed interventions will be reported. After informed consent is obtained and following the administration of study drug, the reporting period for all non-serious AEs and SAEs begins and continues for approximately 5 years or until study discontinuation/termination.

**Study 270-301 Statistical Analysis Plan**

The following types of AEs will be summarized: all AEs, AEs assessed by investigator as related to BMN 270, SAEs, SAEs assessed by investigator as related to BMN 270, AEs leading to study discontinuation, deaths, and events of special interest (EOSI), AEs associated with corticosteroid use, and AEs reported as laboratory abnormalities with clinical significance. Listings will be provided.

If the onset date or end date of an AE is partial, the same imputation rules described in Section 5.6 will be applied.

14.1.1 All Adverse Events

The incidence and number of events for all TEAEs will be summarized by system organ class (SOC), preferred term (PT) and severity. Exposure-adjusted summaries, in which each subject's incidence is divided by the duration of follow-up, will also be provided. For those AEs that occurred more than once during the study, the maximum severity will be used to summarize the AEs by severity. In addition to a TEAE listing, a listing of AEs reported under Investigations SOC will also be provided.

14.1.2 Drug-Related Adverse Events

All TEAEs assessed by investigator as study drug related (i.e., ADRs) will be summarized by SOC, PT and severity.

14.1.3 Deaths and Serious Adverse Events

Serious adverse events and SAEs assessed by investigator as study drug related (i.e., serious ADRs) will be summarized by SOC, PT and severity. Listings of deaths and all SAEs will be provided.

14.1.4 Adverse Events Causing Early Discontinuation

Adverse events that cause early discontinuation of study will be summarized by SOC, PT and severity. In addition, a list of subjects with the AEs resulting in discontinuation of study will be provided.

14.1.5 Events of Interest

The following events of interest, which include EOSI defined in the protocol, will be summarized by PT, if applicable. A list of subjects will be provided for each type of EOSI. AE profile summary including time to event onset from infusion and duration of the events will be generated for EOSI (unless otherwise specified below).

- Transaminitis
 - ALT elevation (Preferred term: "Alanine aminotransferase increased").

Study 270-301 Statistical Analysis Plan

- AEs related to liver function, defined using the MedDRA search strategy high level term (HLT = “Liver function analyses”).
- Potential Hy’s law cases
 - ALT or AST $\geq 3x$ ULN and serum TBL $> 2x$ ULN
 - Assessments of ALT/AST and TBL must be on the same day

A listing will be provided.

- Infusion-related reaction, infusion-associated reaction, Hypersensitivity, Anaphylactic or Anaphylactic reactions
 - Infusion-related reactions, defined as AEs occurring during BMN 270 infusion or within 6 hours post-infusion, will be summarized as follows:
 - Subjects who receive infusion with initial rate of approximately 4 mL/min
 - The rest of the subjects, i.e. subjects who receive infusion with initial rate of 1 mL/min
 - All treated subjects
 - Infusion-associated reactions, defined as AEs occurring within 48 hours post-infusion
 - Systemic hypersensitivity (Hypersensitivity [SMQ] – narrow scope).
 - Anaphylactic, or anaphylactoid reactions (Anaphylactic reaction [SMQ] – algorithmic) – listing only.
- Thromboembolic events:
 - Embolic and thrombotic events (SMQ) for entire study period.
 - AEs suggestive of thromboembolic events: for subjects who have FVIII activity > 170 IU/dL (based on chromogenic assay) any time during study, a listing of clinical terms suggestive of thromboembolic events observed from the time point prior to when FVIII was elevated until FVIII falls below 150 IU/dL. (The preferred terms are listed in Appendix 20.2.)
- Development of anti-FVIII neutralizing antibodies as measured by Nijmegen modified Bethesda Assay (Preferred term: “Anti factor VIII antibody positive”)
- Any new diagnosis of malignancy (except non-melanoma skin cancer)

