Null hypothesis: $\text{post-baseline ABR} - \text{baseline ABR} \geq 0$
6. For superiority of BMN 270 versus FVIII prophylaxis in Haemo-QoL-A Total score
Null hypothesis: $\text{post-baseline total score at Week 104} - \text{baseline total score} \leq 0$
7. For superiority of BMN 270 versus FVIII prophylaxis in Haemo-QoL-A Physical functioning domain score
Null hypothesis: $\text{post-baseline physical functioning score at Week 104} - \text{baseline physical functioning score} \leq 0$

Study 270-301 Statistical Analysis Plan

8. For superiority of BMN 270 versus FVIII prophylaxis in Haemo-QoL-A Consequences of bleeding domain score

Null hypothesis: post-baseline Consequences of bleeding score at Week 104 – baseline Consequences of bleeding score ≤ 0

9. For superiority of BMN 270 versus FVIII prophylaxis in Haemo-QoL-A Role functioning domain score

Null hypothesis: post-baseline Role functioning score at Week 104 – baseline Role functioning score ≤ 0

After the 2-year final analysis, safety and efficacy will then continue to be assessed long-term in all subjects for a total of approximately 5 years.

Safety endpoints and analyses

- Incidence of adverse events (AEs) and serious AEs (SAEs)
- Change in clinical laboratory tests (serum chemistry and hematology)
- Change in vital signs
- Change in physical examination
- Vector shedding (blood, urine, semen, stool, saliva)
- Liver tests (LTs, including ALT, AST, GGT, direct and total bilirubin, lactate dehydrogenase [LDH], and alkaline phosphatase)
- Immune response to FVIII transgene product and AAV5 capsid proteins

Analyses of safety endpoints will be descriptive based on the ITT population. Adverse events (AEs), AEs assessed by the investigator as related to BMN 270, serious adverse events (SAEs), SAEs assessed by the investigator as related to BMN 270, AEs leading to study discontinuation, deaths, AEs related to immunosuppression and events of special interest (EOSI) will be summarized by Medical Dictionary for Regulatory Activities (MedDRA) System Organ Class (SOC) and Preferred Term (PT). AEs and AEs assessed by the investigator as related to BMN 270 will also be summarized by severity. Exposure-adjusted summaries will also be provided. A by-subject listing will be provided for subjects who experience a serious AE (SAE), including death, or experience an AE associated with early withdrawal from the study.

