14.2 Clinical Laboratory Tests

Clinical laboratory tests include blood chemistry, hematology, urine tests, and coagulation. Clinical laboratory test values and change from Baseline will be summarized descriptively by visit. Shift tables cross-tabulating CTCAE v4.03 grade at Baseline vs. worst CTCAE v4.03 grade at post-Baseline visits will be provided as well. A supportive listing of abnormal test values with CTCAE v4.03 grade 3 or greater will be produced.

Liver tests (LTs) by central labs will be assessed on a regular basis, as detailed in the protocol. Boxplots of maximum ALT values at 4-week intervals over time and corresponding line plots will be provided. The same analyses based on mean or median ALT values will be conducted. ALT values and change from Baseline over time will be summarized descriptively. Summaries of ALT elevations including baseline ALT, time from infusion to ALT > ULN, ALT > 3x ULN, ALT > 5x ULN, ALT \geq 1.5x ULN or (> ULN & > 2x baseline value), ALT > 2x baseline value, ALT > 1.5x baseline value, ALT > 1.5x baseline value or > ULN, ALT > 2x baseline value or > ULN, peak ALT level, and duration of ALT elevation will be provided. Correlation of ALT elevation to FVIII levels, as well correlation of steroid treatment to ALT elevation and FVIII levels will be presented in subjects' profile figures. Correlation of alternative immunosuppressant (AIS) treatment to ALT elevation including time to ALT elevation recovery after AIS onset will be summarized. Local ALT assessments will be analyzed similarly as the central ALT assessments, if needed. Similar analyses will be applied to other liver tests including aspartate transaminase (AST), gamma-glutamyl transferase (GGT), lactate dehydrogenase (LDH), bilirubin, and alkaline phosphatase (ALP), if needed.

In addition, incidences of potential drug-induced liver injury (DILI) that include an elevated ALT or AST in combination with either an elevated bilirubin or clinical jaundice, as defined by Hy's law, will be summarized by count and percentage. The profile summary of the related laboratory tests results needed for determination by Hy's law will be provided for the subjects with potential DILI.

Finally, the impact of select concomitant medication use (e.g., lamivudine) on ALT elevations will be assessed in the same manner as outlined in Section 13.3.7 in the mITT subjects who have discontinued them before the data cut-off date for the 2-year analysis.

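### Sections 14.1.5 and 14.2 of the SAP select potential Hy's law/DILI cases by different rules, and the same-day rule can leave out sequential elevations

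*SAP*

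**What the plan says.** Section 14.1.5 (Events of Interest) defines potential Hy's law cases by "ALT or AST $\geq 3x$ ULN and serum TBL $> 2x$ ULN". It adds the condition "Assessments of ALT/AST and TBL must be on the same day" and promises a listing.

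Section 14.2 (Clinical Laboratory Tests) plans a count and percentage of potential drug-induced liver injury (DILI), described as "elevated ALT or AST in combination with either an elevated bilirubin or clinical jaundice, as defined by Hy's law". It gives no multiple of ULN, no time relation between the two elevations and no cross-reference to 14.1.5. For subjects with potential DILI it also plans a profile: "The profile summary of the related laboratory tests results needed for determination by" Hy's law.

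The SAP synopsis puts the transaminases and bilirubin in one panel: "Liver tests (LTs, including ALT, AST, GGT, direct and total bilirubin, lactate dehydrogenase". Appendix 20.1 schedules liver tests 7 days apart to Week 36, 14 days apart to Week 52, 28 days apart to Week 100, and 42 days apart for most visits after Week 104.

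**The concern.** The two sections describe what looks like the same safety event, yet a programmer following each one literally would not select the same subjects. One rule is purely laboratory-based, with thresholds and a same-day condition. The other admits a clinical sign and fixes neither threshold nor timing.

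The same-day condition also works against the purpose of a screen. Bilirubin may cross 2x ULN after the transaminases have come down. If ALT and AST are by then both below 3x ULN, the subject never enters the listing. The sequence is plausible here, because the plan expects ALT elevations treated with immunosuppressants and summarises time to ALT recovery after alternative immunosuppressants start (Section 14.2).

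What is at stake is the completeness of a descriptive listing and its agreement with a descriptive count, in a study where Section 14 asks for particular attention to the liver tests. A subject listed in error can be reviewed and set aside, but a subject never listed is not reviewed by this route.

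**Working it through.** The plan has no figure to reproduce, so the check compares the two definitions as selection rules. The ULN multiples in the cases below are illustrative unless they are the SAP's own thresholds.

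**Case by case**

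1. ALT is 6x ULN at one draw. At the next, ALT is 4x ULN and TBL is 3x ULN. Section 14.1.5 lists the subject, because the second draw meets both thresholds on one day.
2. ALT is 6x ULN at one draw. At the next, ALT and AST are both below 3x ULN and TBL is 3x ULN. Section 14.1.5 does not list the subject. Section 14.2 may or may not count the subject, because it does not say whether elevations on different days combine.
3. ALT or AST is raised with reported clinical jaundice, but no draw shows TBL above 2x ULN together with ALT or AST at or above 3x ULN. Section 14.2 can count the subject; Section 14.1.5 cannot list the subject.
4. ALT and bilirubin are both above ULN but below the 14.1.5 thresholds. Section 14.1.5 does not list the subject. Section 14.2 counts the subject if elevated means above ULN, which it does not state.

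**Two readings of Section 14.2**

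- If 14.2 stands alone, "an elevated ALT or AST in combination with either an elevated bilirubin or clinical jaundice" has no threshold or window, and the count is not reproducible from the text.
- If its mention of Hy's law brings in the 14.1.5 criteria, the jaundice route has no operational counterpart. The same-day condition then governs both outputs, so case 2 appears in neither. The profile does not help, because it is produced only for subjects already flagged.

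Either reading leaves something to settle.

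**Can the number missed be estimated?**

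Take ALT at or above 3x ULN for A days, TBL above 2x ULN for 14 days starting L days after ALT onset, and draws every T days at a random phase. Then overlap = min(14, max(0, A − L)), and same-day capture = min(1, overlap / T). None of A, L or the 14 days comes from the SAP; only T = 7 or 14 does.

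- A = 14, L = 10, 12, 14: overlaps are 4, 2 and 0 days. With T = 7, capture is 4/7 = 57%, 2/7 = 29% and 0%. With T = 14, it is 4/14 = 29%, 2/14 = 14% and 0%.
- A = 14, L = 7, T = 7: overlap is 7 days, and capture is 7/7 = 100%.
- A = 28, L = 10 to 14: overlap is 14 days, and capture is 100% with T = 7 or T = 14.

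Plausible-looking inputs span 0% to 100%. The model shows that a miss is possible, but it does not give a rate.

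**The case against.** The best defence is that same-day pairing is clear and reproducible, and that the shared panel makes same-day values the normal situation. Section 14.2 can be read as counting the 14.1.5 cases and adding jaundice. Section 14.1.5 also says that its events include those defined in the protocol, which is not at hand, so the criterion may originate there. Other planned outputs (the CTCAE shift tables, the listing of grade 3 or greater values, the ALT elevation summaries) would show individual abnormal values. All of this stands, but those outputs do not pair ALT/AST with bilirubin, and the jaundice route still has no counterpart in 14.1.5.

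Three stronger readings are tempting and are not supported:

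- A reader might infer that 14.2 contradicts the same-day rule. It does not: 14.2 is silent on timing. The demonstrable mismatch is the jaundice route, the absent thresholds and the absent window.
- A reader might infer that every subject whose bilirubin rises after the transaminase peak is missed. Case 1 shows otherwise. Only subjects with ALT and AST both below 3x ULN at every draw with TBL above 2x ULN are missed.
- A reader might see a separate gap when ALT comes from a local draw and bilirubin from a later central one, given that "Local ALT assessments will be analyzed similarly as the central ALT assessments, if needed". A central draw normally carries its own ALT and AST, so such a subject is missed only if both have already fallen below 3x ULN, which is case 2 again. Section 14.1.5 does not restrict the listing to central results.

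**Conclusion.** The point holds as a definitional mismatch with one identifiable blind spot. The 14.1.5 listing and the 14.2 count can select different subjects, and the same-day rule omits sequential elevations of the kind in case 2. Scheduled liver tests are 7 to 42 days apart, so that sequence can occur, more readily where visits are widely spaced. How often it would occur cannot be stated from the SAP, and the capture percentages in the working should not be quoted as an estimate of missed cases.

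Safety analyses are descriptive under Section 14, so no endpoint, error rate or hypothesis test changes. This is a cheap improvement to a safety screen. It remains worthwhile because the note to file, which says it sets out all changes to the 2-year analysis methods, leaves this definition untouched, and safety follow-up continues to about 5 years.

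**What to change.** Write one analysis definition and have both sections refer to it:

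- Keep the 14.1.5 thresholds: ALT or AST at least 3x ULN and TBL above 2x ULN.
- State whether reported clinical jaundice can stand in for the TBL criterion, and apply that choice to both the listing and the count.
- Pair a qualifying ALT or AST value with a TBL elevation on the same day or within a pre-stated interval afterwards. Thirty days is one example of a screening window for the analysis; it does not come from the SAP.
- Flag same-day cases as a subset, so the current listing can still be recovered.

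The cost is SAP wording and one reprogrammed listing. The downside is that a few extra subjects would be listed for medical review.
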